11.0 DATA SAFETY MONITORING PLAN

In compliance with the Washington University Institutional Data and Safety Monitoring Plan, the Data and Safety Monitoring Committee (DSMC) will meet to review toxicity data at least every 6 months following the activation of the first secondary site. The report will be prepared by the statistician and will be submitted to the Quality Assurance and Safety Monitoring Committee (QASMC). This report will include:

- HRPO protocol number, protocol title, Principal Investigator name, data coordinator name, regulatory coordinator name, and statistician
- Date of initial HRPO approval, date of most recent consent HRPO approval/revision, date of HRPO expiration, date of most recent QA audit, study status, and phase of study
- History of study including summary of substantive amendments; summary of accrual suspensions including start/stop dates and reason; and summary of protocol exceptions, error, or breach of confidentiality including start/stop dates and reason
- Study-wide target accrual and study-wide actual accrual including numbers from participating sites
- Protocol activation date at each participating site
- Average rate of accrual observed in year 1, year 2, and subsequent years at each participating site
- Expected accrual end date and accrual by site
- Objectives of protocol with supporting data and list the number of participants who have met each objective
- Measures of efficacy
- Early stopping rules with supporting data and list the number of participants who have met the early stopping rules
- Summary of toxicities at all participating sites
- Abstract submissions/publications
- Summary of any recent literature that may affect the safety or ethics of the study

Until such a time as the first secondary site activates this protocol, a semi-annual DSM report to be prepared by the study team will be submitted to the QASM Committee beginning 6 months after study activation at Washington University.

The study principal investigator and Research Patient Coordinator will monitor for serious toxicities on an ongoing basis. Once the principal investigator or Research Patient Coordinator becomes aware of an adverse event, the AE will be reported to the HRPO and QASMC according to institutional guidelines.

A DSMC will consist of no fewer than 3 members including 2 clinical investigators and a biostatistician. Like investigators, DSMC members are subject to the Washington University School of Medicine policies regarding standards of conduct. Individuals invited to serve on the DSMC will disclose any potential conflicts of interest to the trial principal investigator and/or appropriate university officials, in accordance with institution policies. Potential conflicts that develop during a trial or a member's tenure on a DSMC must also be disclosed.

Refer to the Washington University Quality Assurance and Data Safety Monitoring Committee Policies and Procedures for full details on the responsibilities of the DSMC at http://www.siteman.wustl.edu/uploadedFiles/Research_Programs/Clinical_Research_Resources/Protocol_Review_and_Monitoring_Committee/QASMCQualityAssurance.pdf

12.0 AUDITING

Since Washington University is the coordinating center, each site will be audited annually by Siteman Cancer Center personnel (QASMC) unless the outside institution has an auditing mechanism in place and can provide a report. The outside sites will be asked to send copies of all audit materials, including source documentation. The audit notification will be sent to the Washington University Research Patient Coordinator, who will obtain the audit materials from the participating institution.

Notification of an upcoming audit will be sent to the research team one month ahead of the audit. Once accrual numbers are confirmed, and approximately 30 days prior to the audit, a list of the cases selected for review (up to 10 for each site) will be sent to the research team. However, if during the audit the need arises to review cases not initially selected, the research team will be asked to provide the additional charts within two working days.

Additional details regarding the Auditing Policies and Procedures can be found at <https://siteman.wustl.edu/wp-content/uploads/2015/QASMC-Policies-and-Procedures-03.31.2015.pdf>

13.0 MULTICENTER REGULATORY REQUIREMENTS

Washington University requires that each participating site sends its informed consent document to be reviewed and approved by the Washington University Regulatory Coordinator (or designee) prior to IRB/IEC submission.

Site activation is defined as when the secondary site has received official written documentation from the coordinating center that the site has been approved to begin enrollment. At a minimum, each participating institution must have the following documents on file at Washington University prior to study activation:

- Documentation of IRB approval of the study in the form of a letter or other official document from the participating institution's IRB. This documentation must show which version of the protocol was approved by the IRB.
- Documentation of IRB approval of an informed consent form. The consent must include a statement that data will be shared with Washington University, including the Quality Assurance and Safety Monitoring Committee (QASMC), the DSMC (if applicable), and the Washington University study team.
- Documentation of FWA, signed FDA Form 1572 (if applicable), and the CVs of all participating investigators.
- Protocol signature page signed and dated by the investigator at each participating site.

The coordinating center Principal Investigator (or designee) is responsible for disseminating to the participating sites all study updates, amendments, reportable adverse events, etc. Protocol/consent modifications and IB updates will be forwarded electronically to the secondary sites within 4 weeks of obtaining Washington University IRB approval. Activated secondary sites are expected to submit protocol/consent/IB modifications to their local IRBs within 4 weeks of receipt unless otherwise noted. Upon the secondary sites obtaining local IRB approval, documentation of such shall be sent to the Washington University study team within 2 weeks of receipt of approval.

Documentation of participating sites' IRB approval of annual continuing reviews, protocol amendments or revisions, all SAE reports, and all protocol violations/deviations/exceptions must be kept on file at Washington University.

The investigator or a designee from each institution must participate in a regular conference call to update and inform regarding the progress of the trial.

14.0 STATISTICAL ANALYSIS METHODS AND SAMPLE SIZE

14.1 Analysis Populations

Intent-to-Treat - The intent-to-treat (ITT) population will be defined as all patients who receive at least one dose of decitabine.

Efficacy-Evaluable - The efficacy-evaluable (EE) population will be defined as all patients who receive at least one cycle of treatment.

Safety - The safety population will be defined as all patients with at least one dose of decitabine.

14.2 Statistical Analysis

14.2.1 Descriptive Analyses

Patient Disposition: The number of patients discontinued, the reasons for discontinuation, and the number of cycles administered will be summarized.

Demographics and Baseline Characteristics: Descriptive summary statistics will be provided for demographic and important baseline characteristics. For continuous variables, the number of patients, mean, standard deviation, median, minimum and maximum will be provided. For categorical variables, the number and percent of patients in each demographic/characteristic category will be summarized.

14.2.2 Primary Endpoint Analysis

The primary end-point of this phase II study is the correlation biomarkers with overall response in AML/MDS patients to decitabine.

We will correlate the presence of patient specific mutations (especially mutations in *DNMT3A*, *IDH1*, *IDH2*, and *TET2*) with overall response rates. Mutation rates in these genes and in other patient-specific genes will be correlated with overall response and their respective 95% confidence intervals will be provided.

Statistical considerations. The relationship between AML/MDS-associated mutations and the responsiveness to decitabine will be described by contingency tables and assessed using Chi-square test or Fisher's exact test as appropriate. The differentially expressed genes between responders and non-responders will be determined using the significance analysis of microarray (SAM). Multivariate logistic regression will also be fit to adjust the potential confounding effects of other demographic and clinical characteristics. The resultant critical *P* values will be corrected for multiple testing. Since the Bonferroni correction is known to be too conservative, a permutation analysis (e.g., 10,000 random assignments for

responsive status) will be used to derive an empirical critical P value. The new critical p-value is the number of permutation tests which yield a lower p-value than the original test divided by the total number of permutation tests.[61]

A power analysis was performed using Chi-square test for the association between mutation and response to decitabine. The frequency of *DNMT3A*, *IDH1/2*, and *TET2* mutations in AML and MDS patients are each between 15% and 30% in multiple cohorts.[29-37] **Table 3** shows the minimal detectable differences of response rates between mutant and wild-type cases, assuming an expected overall 45% CR/CRi rate and 80% power. For an average of 20% frequency of a mutated gene, for example, 100 patients will provide 80% power to detect 30% difference at a 2-sided 0.1 alpha error. The purpose of this study is to determine whether any of these mutations result in a clinically significant association that would warrant pre-treatment testing. We believe that a reasonable cut off would be if at least 30% of clinical response could be attributed to the presence of a specific mutation. However, we anticipate that more power could be achieved as we assess patient groups with combined characteristics (e.g. *DNMT3A* mutation or loss of *DNMT3A* expression). In addition, we expect that the majority of the enrolled 125

Table 3. Detectable mutation associated response rates (80% power, $\alpha = 0.05$)

Total N	% of patients with a given mutation	Detectable response difference	Sensitivity of mutation to predict response at minimum detectable response difference*
100	15%	0.40	80%
	20%	0.35	75%
	30%	0.30	67%
	40%	0.27	61%
	50%	0.26	58%

* Assuming the overall response rate (CR/CRi) of 45%

patients can be used in the analysis (since all of our molecular information will be acquired within 30 days of enrollment, we anticipate a drop-out rate of 20% or less).

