We and others have recently used whole genome sequencing to identify recurrent, somatic mutations in AML and MDS patients in four genes that are involved in methylcytosine regulation: *DNMT3A*, *IDH1*, *IDH2*, and *TET2*. [29-37] Collectively, nearly half of all AML/MDS patients have a mutation in one of these four genes. *DNMT3A* mutations are associated with an adverse outcome in AML patients treated with cytotoxic chemotherapy. [35, 38] However, it is not yet clear whether the presence of mutations in one or more of these genes is associated with response or resistance to decitabine.

In this study, we will treat patients with the current state-of-the-art decitabine schedule. [3] We will perform exome sequencing on all patients and correlate response with mutation status, rate of mutation clearance, expression profile, plasma decitabine levels, and DNA

methylcytosine content reduction. This approach will comprehensively assess genomic and pharmacologic parameters that could clinically predict patient response to decitabine.

In this study, we will combine analysis of patients with AML and MDS. Recent genomic analysis has shown that AML and MDS have shared mutations in many of the same genes, shared patterns of mutation acquisition, and shared patterns of mutation evolution.[39, 40] Furthermore, MDS, like AML, presents with clonal hematopoiesis, even when the morphologic blast count is zero.[36] Because this study will identify and track the rate of clearance of patient specific mutations, and because decitabine has been shown to have efficacy in both AML and MDS patients, [2, 3, 16-19, 41-45] combining analysis of AML and MDS patients is reasonable. Asymptomatic MDS patients are excluded because these patients are typically followed with watchful-waiting rather than with chemotherapy.

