14.2.5 Description of Planned Subgroup Analyses

The following subgroups (if sufficient numbers of patients) will be explored with respect to the primary and overall survival endpoints.

- Age (60-69 years old vs ≥ 70 years old)
- Cytogenetics
- Patients with AML-associated mutations in *DNMT3A*, *TET2*, *IDH1*, or *IDH2* vs those who do not have somatic variants in these genes.

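### The per-gene mutation-response test pools AML and MDS without stratification, so it is confounded by diagnosis if both gene frequency and response rate differ between the two diseases

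*Combined protocol and SAP*

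**What the plan says.** Section 1.1 states that "we will combine analysis of patients with AML and MDS" and concludes that "combining analysis of AML and MDS patients is reasonable". Its grounds are shared mutated genes, shared patterns of mutation acquisition and evolution, and decitabine activity in both diseases.

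Section 14.2.2 says the association between mutation and response "will be described by contingency tables and assessed using Chi-square test" or, where suitable, Fisher's exact test. No stratification factor is named. For multiple testing it plans "a permutation analysis (e.g., 10,000 random assignments for" response status, with no restriction within disease. It adds: "Multivariate logistic regression will also be fit to adjust the potential confounding effects of other demographic and clinical characteristics". The covariates are not listed, and diagnosis is not mentioned.

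The power calculation in the same section uses one response rate (45%) for the pooled population and one gene-frequency range (15% to 30%).

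Sections 9.1 and 9.2 score response differently. AML has a CRi category; MDS has marrow CR and no CRi. The rules on haemoglobin, transfusion and residual dysplasia also differ.

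Section 14.2.5 opens with "The following subgroups (if sufficient numbers of patients) will be explored with respect to the primary and overall survival endpoints" and lists age, cytogenetics and four-gene mutation status. AML v MDS is not on the list. The wording of 14.2.2 and 14.2.5 on these points is the same in every protocol version in the file.

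**The concern.** Diagnosis is known before treatment and may be related to both sides of the primary table. Response criteria differ by disease, so a difference in response rate is plausible from the plan's own definitions. Section 1.1 argues that the same genes are mutated in both diseases. It does not say that they are mutated equally often, or that the response rates are equal.

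If both differ, carriers and non-carriers contain different proportions of AML. Part of the observed response difference then belongs to the disease, not the mutation. Unrestricted shuffling of response breaks the link between response and diagnosis as well, so it tests the wrong null hypothesis. At stake is a false lead for a gene with no effect in either disease, or a true predictor that is diluted or exaggerated. The trial is meant to decide whether a mutation justifies testing before treatment, so it also matters whether a finding applies to AML, MDS or both.

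**Working it through.** **1. The plan's own figure.** The text says "100 patients will provide 80% power to detect 30% difference at a 2-sided 0.1 alpha error", with 20% mutated and 45% overall response. Carriers then respond at 0.45 + 0.8 × 0.30 = 0.69 and non-carriers at 0.45 − 0.2 × 0.30 = 0.39, with 20 and 80 patients.

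Power = Φ{[0.30 − 1.645 √(0.45 × 0.55 × (1/20 + 1/80))] / √(0.69 × 0.31/20 + 0.39 × 0.61/80)} = Φ{(0.300 − 0.205)/0.117} = 79.3%.

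The stated 80% is reproduced. Table 3 uses alpha 0.05, where the same example has 68.5% power, so type I error is shown below at both levels.

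**2. Spurious difference when the gene has no effect in either disease.**

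Difference = [P(AML | carrier) − P(AML | non-carrier)] × (AML response − MDS response).

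The difference is zero if either bracket is zero. The AML share (60%), gene frequencies and response rates by disease are all assumptions.

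- Carriers 30% AML, 15% MDS: AML share is 0.18/0.24 = 0.750 in carriers and 0.42/0.76 = 0.553 in non-carriers, a gap of 0.197. Response gaps of 12.5, 25 and 37.5 points give 2.5, 4.9 and 7.4 points.
- Carriers 25% v 20%: 0.15/0.23 − 0.45/0.77 = 0.068. A 25-point response gap gives 1.7 points.

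**3. Type I error.** Simulated, 40,000 trials per row, N = 100, 60% AML: pooled Pearson chi-square against the Cochran-Mantel-Haenszel (CMH) test stratified by diagnosis, without continuity correction. Repeat runs differ by up to 0.4 points.

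| Carriers AML v MDS | Response AML v MDS | Pooled, nominal 5% | Pooled, nominal 10% |
|---|---|---|---|
| 30% v 15% | 45% v 45% | 5.2% | 10.1% |
| 20% v 20% | 55% v 30% | 5.2% | 10.2% |
| 25% v 20% | 55% v 30% | 5.4% | 10.4% |
| 30% v 15% | 50% v 37.5% | 5.6% | 10.8% |
| 30% v 15% | 55% v 30% | 7.5% | 13.3% |
| 30% v 15% | 60% v 22.5% | 10.2% | 17.2% |

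The stratified test stays within about 0.2 points of nominal in every row.

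**4. Permutation.** A separate simulation used a 50:50 disease mix, 1,500 trials and 400 permutations each, at nominal 5%. With carriers 30% v 15%, shuffling across all patients gives 5.7% at a 20-point response gap and 6.5% at 30 points; shuffling within disease gives 3.9% and 3.3%. The simulation standard error is √(0.05 × 0.95/1500) ≈ 0.6 points, so within this frequency range the excess is small. For a gene carried by 40% v 5%, outside the plan's range but possible among the other genes to be tested, the figures at a 30-point gap are 22.3% and 3.9%.

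**5. Power for a true 30-point effect in both diseases** (N = 100, 60% AML, alpha 0.10).

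| Carriers AML v MDS | Wild-type response AML v MDS | Expected pooled difference | Pooled power | CMH power |
|---|---|---|---|---|
| 15% v 28% | 50% v 28% | 25.7 points | 67% | 79% |
| 17% v 23% | 48% v 38% | 29.1 points | 76% | 78% |
| 28% v 15% | 50% v 28% | 33.9 points | 90% | 83% |
| 20% v 20% | 39% v 39% | 30.0 points | 78.4% | 78.0% |

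Overall response in the first row is 0.6 × 0.545 + 0.4 × 0.364 = 47%, close to but not exactly the plan's 45%.

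**The case against.** Pooling is a disclosed and reasoned choice in a single-arm Phase II biomarker study, and confounding is not ignored. A logistic regression is planned under the primary endpoint to adjust for clinical characteristics, and diagnosis is one. The multiple-testing sentence follows it directly and could be read as covering the model too. This stands in part: the plan does not rank the table above the model. But the covariates are unnamed, and a model fitted in addition does not alter the table's p-value or an unrestricted permutation.

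The inputs are also assumed. The 15% to 30% range runs over genes and cohorts and is not an AML v MDS contrast; giving its two ends to the two diseases takes the widest spread. The adverse-karyotype or TP53 eligibility rule in two of the protocol versions makes it less certain that the range describes the patients enrolled. This stands, and it is why a mild imbalance is shown as well.

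Finally, the practical effect is limited. In the three scenarios with carriers 30% v 15% and unequal response, a null gene that is significant at 0.10 and also shows at least a 30-point advantage occurs in 1.1%, 1.7% and 2.7% of trials. This also stands.

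A reader might go further and infer that a gene merely commoner in one disease will look predictive. It will not: with equal response rates the pooled test holds its level. Nor do the documents support saying that pooling always masks real effects, since the reverse imbalance inflates power.

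**Conclusion.** The point holds conditionally. The test and permutation as described do not control for diagnosis, and they are confounded if gene frequency and response rate both differ between AML and MDS. The documents show neither difference. Differing response criteria make the second plausible; nothing in them establishes the first.

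Under the assumptions used, the false-positive excess ranges from negligible to about a doubling of a nominal 5%, and only the widest imbalance reaches the top of that range. The effect on power is the larger concern: about 12 points lost or 7 gained, depending on direction, in a design with about 79% power at alpha 0.10. Severity is modest and confidence moderate, because the mechanism is certain but every driver of its size is assumed.

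**What to change.** In 14.2.2, make the per-gene test a Cochran-Mantel-Haenszel test, or an exact conditional test where counts are small, stratified by entry diagnosis (AML or MDS). At minimum, name diagnosis as a required covariate in the logistic model. Permute response within diagnosis. Report the common odds ratio, each disease's estimate with its confidence interval, and a homogeneity test. Add AML v MDS to 14.2.5.

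The cost is SAP wording and a few lines of code. Section 15.0 already requires the Disease Diagnosis Form before treatment starts, so no new data are needed. With no imbalance, stratifying costs under 1 point of power (78.4% to 78.0%).

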1.3 Correlative Studies

All correlative studies will be collected under HRPO# 201011766 (“Tissue Acquisition for Analysis of Genetic Progression Factors in Hematologic Diseases”) that all patients will be concurrently enrolled in. The goals of the correlative studies include:

1. To correlate patient-specific mutations with response to decitabine.
We will perform exome sequencing of each patient’s pre-study bone marrow sample and skin sample. We will determine AML/MDS-associated variants found in the bone marrow, but not skin sample. We will correlate the presence of mutations with response (especially mutations in *DNMT3A*, *IDH1*, *IDH2*, and *TET2*). This study is powered to identify mutations with >80% sensitivity to predict decitabine response if used as a clinical assay.
2. To correlate the velocity and depth of response with response to decitabine.
We will assess tumor burden by allele frequency of patient-specific mutations in bone marrow samples collected pre study, Cycle 1 Day 10±1, Cycle 1 Day 28±4, and Cycle 2 Day 28±4. We will assess mutations in at least 24 recurrently mutated genes (including, but not limited to: *FLT3*, *DNMT3A*, *NPM1*, *TET2*, *WT1*, *IDH1*, *IDH2*, *RUNX1*, *NRAS*, *TP53*, *U2AF1*, *KRAS*, *PHF6*, *MSTP9*, *PTPN11*, *KIT*, *SMC3*, *PRUNE2*, *ETV6*, *CEBPA*, *SMC1A*, *ASXL1*, *STAG2*, *RAD21*) as well as all patient-specific mutations discovered during exome sequencing. The leukemic allele frequency will be measured using the Illumina MySeq or HiSeq platform using DNA capture by gene specific biotinylated-oligonucleotides. Patient bone marrow samples will be assessed pre-study, Cycle 1 Day 10 ± 1, Cycle 1 Day 28 ± 4, and Cycle 2 Day 28 ± 4 and compared with patient specific skin samples (normal control). The velocity of response will be calculated as the natural log rate of patient-specific mutation allele frequency clearance. Depth of response will be defined as the lowest patient-specific mutation

allele frequency in a bone marrow sample. The velocity and depth of tumor response will be correlated to:

- Achievement of clinical CR,
- Time to best response,
- Mutational status,
- Time to disease progression.

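### Adjusted logistic models for rare genes have no finite odds ratio when all or none of the carriers respond, and Section 14.2.2 provides no method that copes with this

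*Combined protocol and SAP*

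**What the plan says.** Section 14.2.2 (Primary Endpoint Analysis) first compares mutation status with response in contingency tables, "assessed using Chi-square test or Fisher's exact test as appropriate". It then adds: "Multivariate logistic regression will also be fit to adjust the potential confounding effects of other demographic and clinical characteristics". The next sentence is "The resultant critical *P* values will be corrected for multiple testing", to be done by permuting response status.

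The gene set is open-ended. The section emphasises DNMT3A, IDH1, IDH2 and TET2, but also states: "Mutation rates in these genes and in other patient-specific genes will be correlated with overall response and their respective 95% confidence intervals will be provided". Section 1.3 shows how long the list may be: "We will assess mutations in at least 24 recurrently mutated genes", plus all mutations discovered by exome sequencing.

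The plan does not state a minimum carrier count, an estimator or test for the logistic model, its covariates, which genes receive an adjusted model, what to do if the model separates, whether the table or the adjusted result decides, or which p-value is permuted.

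**The concern.** A gene carried by only a few of about 100 patients can easily have carriers who all respond, or who all fail to respond. The logistic likelihood then keeps rising as the gene's coefficient moves towards plus or minus infinity. The software stops at an arbitrary large value with an enormous standard error, so a Wald test reports no association however strong the pattern is.

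The logistic model is the plan's only stated control for confounding, in a single-arm study that pools AML and MDS. For such a gene a reader could be shown p = 0.016 from the table and p = 0.999 after adjustment, with nothing in the plan to explain or resolve the gap.

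**Working it through.** **The plan's own figure.** Inputs from Section 14.2.2: 100 patients, 20% mutated, a 30-point difference, 45% overall response, two-sided alpha 0.10. Wild-type response = 0.45 − 0.20 × 0.30 = 0.39; carrier response = 0.69. The pooled two-proportion formula gives

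z = [0.30 − 1.645 × √(0.45 × 0.55 × (1/20 + 1/80))] / √(0.69 × 0.31/20 + 0.39 × 0.61/80) = 0.0954 / 0.1169 = 0.816,

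so power is 79.3%, against the stated 80%. The drop-out figure also agrees: 125 × 0.80 = 100. N = 100 with 45 responders is therefore a fair base for what follows.

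**When every carrier responds.** Single-gene fits without covariates, k carriers, all responding. The Fisher p-value is C(45,k)/C(100,k). In a two-by-two table the Firth odds ratio adds one half to each cell; for k = 5 it is (5.5 × 55.5)/(0.5 × 40.5) = 15.1.

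| k | Fisher p | ML odds ratio | Wald p | Likelihood-ratio p | Firth odds ratio | Firth p |
|---|---|---|---|---|---|---|
| 4 | 0.038 | infinite | 0.999 | 0.010 | 12.0 | 0.030 |
| 5 | 0.016 | infinite | 0.999 | 0.004 | 15.1 | 0.012 |
| 6 | 0.007 | infinite | 0.999 | 0.0015 | 18.3 | 0.005 |

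With two simulated covariates added (an assumption, since the plan lists none), the Wald p stays at about 0.999 for every k tried from 2 to 20. At k = 5 the likelihood-ratio p is then 0.0019 and the Firth p 0.006.

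**Size of the likelihood-ratio test.** With no association and fixed margins, the number of responding carriers is hypergeometric. The true size is the total probability of the outcomes with nominal p at or below 0.05.

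| k | P(all respond) | P(none respond) | Likelihood-ratio p, all / none | Firth p, all / none | Size, likelihood-ratio | Size, Firth |
|---|---|---|---|---|---|---|
| 3 | 0.088 | 0.162 | 0.027 / 0.056 | 0.070 / 0.152 | 8.8% | 0% |
| 4 | 0.038 | 0.087 | 0.010 / 0.027 | 0.030 / 0.080 | 12.5% | 3.8% |
| 5 | 0.016 | 0.046 | 0.004 / 0.013 | 0.012 / 0.042 | 6.2% | 6.2% |
| 6 | 0.007 | 0.024 | 0.0015 / 0.006 | 0.005 / 0.021 | 8.8% | 3.1% |

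At k = 6 the likelihood-ratio test also rejects for 5 of 6 responding (probability 0.056, p = 0.046). At k = 5 the two tests have the same size.

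**How often it happens.** The 15% row of Table 3 implies a carrier response of 0.45 − 0.15 × 0.40 + 0.40 = 0.79. Applying that rate to rarer genes is an assumption. All carriers then respond with probability 0.79^k: 39%, 31% and 24% for k = 4, 5 and 6. With no effect, all or none respond with probability 0.45^k + 0.55^k: 13%, 7% and 4%. For the named genes it is 0.79^15 = 2.9% at 15 carriers and 0.73^20 = 0.2% at 20. If the 15% row's difference ran the other way, carriers would respond at 0.51 − 0.40 = 0.11, and none of 15 would respond with probability 0.89^15 = 17%; the 20% row gives 0.83^20 = 2%.

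**Permutation.** The plan's rule reads "The new critical p-value is the number of permutation tests which yield a lower p-value than the original test", divided by the total number. With 2,000 permutations and all carriers responding, applying it to the Wald p gives 0.97 at k = 5 and 1.00 at k = 10. Applied to the Fisher p, no permutation was lower at k = 5, 8 or 10.

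**The case against.** The strongest reply is that the plan already handles sparse genes: the first-named test is Fisher's exact test where appropriate, logistic regression is only an addition, and nothing lets the adjusted result override the table. That stands. A reader might infer that the strongest rare-gene signals vanish from the trial; the Fisher p-values above show that they do not.

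Three other stronger readings also fail. That every gene receives its own adjusted model, tested by Wald, is an inference, because the plan names neither. That a promised 95% interval is lost misreads the section: the interval sentence concerns mutation rates and overall response, comes before the logistic sentence, and promises nothing for an adjusted odds ratio. That the permutation reference is distorted holds only if adjusted Wald p-values are permuted, and the plan does not say which p-value is used.

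It can also be said that a likelihood-ratio test on the ordinary model rescues the analysis. In part it does. Its p-values are small, and the ordinary profile interval has a finite lower limit (odds ratio 2.1, 2.8 and 3.6 for k = 4, 5 and 6, no covariates). But it still gives no finite estimate, and its size is above nominal for every k from 3 to 6. A sound permutation of that statistic could correct the size, but the plan does not commit to one.

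**Conclusion.** The point holds in a limited form and is minor. Section 14.2.2 prescribes logistic adjustment with rare genes in scope and no carrier minimum. Under separation, ordinary maximum likelihood gives no finite adjusted odds ratio, the Wald p-value is about 1, and the uncorrected likelihood-ratio test has size of about 6% to 12.5% for 3 to 6 carriers. Only adjusted results for rare genes are at stake. The four named genes are almost unaffected in the direction Table 3 describes, where carriers respond more often; a resistance mutation at the bottom of the 15% to 30% range would be the exception.

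This rests on N = 100 with 45 responders. The size figures come from the unadjusted model with fixed margins, and the 24% to 39% frequencies borrow the 79% response rate from Table 3, since the documents give no effect size for genes with 4 to 6 carriers.

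**What to change.** Add to Section 14.2.2: adjusted gene models will be fitted by Firth penalised logistic regression, with penalised-likelihood-ratio p-values and profile penalised-likelihood intervals, and the same fit will be used in the permutations wherever adjusted p-values are permuted. The same sentence should say which p-value is permuted.

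The cost is one sentence, slight shrinkage of the odds ratios and a little more computing, all in standard software. Intervals for rare genes will remain very wide (about 1.6 to 2,000 for 5 of 5 carriers, without covariates), but with a finite estimate and a usable lower limit. Exact logistic regression would be a reasonable alternative. A minimum carrier count would also avoid the failure, at the price of leaving the rarest genes unadjusted.
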